2.1.4.1 Adverse events variables

Adverse event observation period

- Treatment-emergent adverse events are adverse events that developed or worsened or became serious during the treatment-emergent adverse event period in the open-label period of the study.
- Posttreatment adverse events are adverse events that developed or worsened or became serious during the posttreatment period in the open-label period of the study.

All adverse events, including serious adverse events (SAEs) and adverse events of special interest (AESI) will be coded to a lower-level term (LLT), preferred term (PT), high-level term (HLT), high-level group term (HLGT), and associated primary system organ class (SOC) using the version of Medical Dictionary for Regulatory Activities (MedDRA) currently in effect at Sanofi at the time of database lock.

Record the occurrence of adverse events (including serious adverse events and AESI) from the time of signed informed consent until the end of the study.

AESIs include the following terms:

- Gastrointestinal disorders (Nausea and diarrhea)
- Hepatic disorders
- Pancreatic disorders
- Bone marrow disorders
- Infections and Infestations
 - A specific analysis of Covid-19 related adverse events will be performed, using the search terms described in Appendix D
- Hypersensitivity
- Severe skin reaction
- Malignancy
- Hypertension
- Cardiac Arrhythmias
- Pulmonary disorders (ILD)
- Embolic and Thrombotic
- Hemorrhage
- Peripheral neuropathy
- Convulsions
- Alopecia
- Psychiatric disorders

Additional AESIs may be identified through the ongoing studies. The complete list of AESIs and details of the grouping algorithm will be finalized prior to the Database Lock (DBL).

2.1.4.2 Deaths

The deaths observation periods are per the observation periods defined above.

- Death on-study: deaths occurring during the on-study observation period

- Death on-treatment: deaths occurring during the treatment-emergent adverse event period
- Death post-study: deaths occurring after the end of the study (ie, the end of open-label period)

2.1.4.3 Laboratory safety variables

Clinical laboratory data consists of blood analysis, including hematology, clinical chemistry, and urinalysis. Clinical laboratory values after conversion will be analyzed into standard international units and international units will be used in all listings and tables.

Blood samples for routine clinical laboratories will be taken at Screening, randomization, Weeks 4, 12 and then every 12 weeks up to the EOT (Week 96, premature treatment discontinuation visit and the time when patient switches to the open label period after a clinical confirmed relapse or high MRI activity whichever comes first) in the double-blind period, and then at transition, Weeks 4, 12 and then every 12 weeks up to the EOT (Week 192 or premature treatment discontinuation visit whichever comes first) in the open-label period. The laboratory parameters will be classified as follows:

- Hematology
 - **Red blood cells and platelets and coagulation:** hemoglobin, hematocrit, mean corpuscular hemoglobin, red blood cell count, platelet count, prothrombin time, activated partial thromboplastin time
 - **White blood cells:** white blood cell count, neutrophils, lymphocytes, monocytes, basophils, eosinophils
- Clinical chemistry
 - **Metabolism:** glucose, cholesterol, triglycerides, total protein, albumin, globulin, albumin/globulin ratio, creatine phosphokinase(CPK), serum amylase and lipase
 - **Electrolytes:** sodium, potassium, chloride, calcium, inorganic phosphorus, bicarbonate, magnesium
 - **Renal function:** creatinine, creatinine clearance, blood urea nitrogen (BUN), uric acid
 - **Liver function:** alanine aminotransferase(ALT), aspartate aminotransferase(AST), alkaline phosphatase, Gamma Glutamyl Transferase(GGT), lactate dehydrogenase (LDH), total bilirubin, direct/indirect bilirubin
 - **Pregnancy test:** Serum β -human chorionic gonadotropin (β -HCG) for pubescent females (NOTE: This test is performed at screening, randomization and then every 12 weeks and EOT in the double-blind period, and then every 12 weeks and EOT in the open-label period)
- Urinalysis - quantitative analyses: pH, ketones, protein, glucose, blood, urobilinogen, bilirubin, microscopic sediment and specific gravity

The following safety laboratory testing will be conducted in between clinical routine lab at Weeks 8, 16, 20, 30 and then every 12 weeks up to the EOT in the double-blind period, and then at Weeks 8, 16, 20, 30 and then every 12 weeks up to EOT in the open-label period measuring

- Hematology (as above)
- Liver function tests (ALT, AST, GGT, total bilirubin, and direct/indirect bilirubin)
- Pancreatic enzymes (serum amylase and lipase).

At EOT +2 weeks and EOT +4 weeks:

- Uric acid and inorganic phosphorus will also be performed.

Laboratory assessment for TSH will also be performed at randomization, every 24 weeks and EOT in the double-blind period, and then at Week 96 and EOT in the open-label period.

Technical formulas are described in [Section 2.5.1](#).

2.1.4.4 Vital signs variables

Vital signs include: radial heart rate, systolic and diastolic blood pressure (standing and supine) and body temperature. Weight and height will be documented in the growth charts.

2.1.4.5 Electrocardiogram variables

A standard 12-lead ECG will be performed at randomization, EOT in the double-blind period and EOT in the open-label period and will be evaluated centrally.

ECG parameters include heart rate, PR interval, QRS interval, QT, and corrected QTc (QTc interval calculated by Bazett's method) and QTcF (QTc interval calculated by Fridericia's method).

2.1.4.6 Tanner scales

The Tanner scale (also known as the Tanner Stages I-V) will be used to define physical measurements of growth and development ((including sexual development and endocrine function), based on external primary and secondary sex characteristics, such as the size of the breasts, genitalia, and development of pubic hair.

Tanner stage will be performed at baseline, every 24 weeks and EOT (until the patient completes sexual maturity (defined by Tanner Stage 5).

2.1.5 Pharmacokinetic variables

Blood samples will be collected at Week 2, 3 and 4 (PK run-in [8 weeks] period), 12, 24, 36 and EOT visit or in case of overdose in the double-blind and open-label period. An additional sample may be required during the PK run-in period in case of inadequate sampling or information/variability.

2.1.6 Immunoglobulins

Serum immunoglobulins concentration (IgG, IgM and IgA) will be performed at randomization and every 24 weeks up to Week 96/EOT in the double-blind period, and then at Week 96 and Week 192/EOT in the open-label period.

In addition if a patient has a vaccination, antibody titers will be assessed before and after vaccination (only inactivated vaccines are allowed).

2.2 DISPOSITION OF PATIENTS

This section describes patient disposition for both patient study status and the patient analysis populations.

All the tables in this section will be presented by the treatment groups the patients were allocated to in the double-blind and open-label period (placebo/teriflunomide versus teriflunomide/teriflunomide) as well as the overall treatment group.

Enrolled patients are defined as any patient who entered the open-label period and where signed informed consent/assent was re-obtained from the patient and patient's legal representative (parents or guardians) according to local regulations when they enter the open-label period of the study.

For patient study status, the total number of patients in each of the following categories will be presented in the clinical study report using a flowchart diagram or summary table:

- Patients who were randomized and treated in the double-blind period
- Patients who completed the double-blind period
- Patients who discontinued from the double-blind period
- Enrolled patients in the open-label period
- Patients who enrolled but were not treated in the open-label period
- Patients who completed the open-label treatment period
- Patients who discontinued open-label treatment period
- Patients who discontinued open-label treatment by main reason for permanent treatment discontinuation in the open-label period
- Patient's decision to permanently discontinue the treatment in the open-label period.

For all categories of patients, percentages will be calculated using the number of enrolled patients as the denominator. Reasons for treatment discontinuation will be supplied in tables giving numbers and percentages by treatment group.

The Covid-19 related disposition information will be summarized separately including number of patients were impacted by the Covid-19, Covid-19 related reasons for permanent treatment discontinuation. The summary of disposition by visit impacted by the Covid-19 will be summarized if applicable.

Patients who did not complete the study and for whom no end-of-treatment data are available will be considered as lost to follow-up.

All critical or major deviations potentially impacting efficacy analyses, drug-dispensing irregularities, and other major or critical deviations will be summarized in tables giving numbers and percentages of deviations by treatment group. The critical or major deviations that related to the Covid-19, regardless of deviation categories, will be summarized by treatment group separately.

Kaplan-Meier estimates of the cumulative incidence of permanent IMP discontinuation for any reason will be provided for open-label period. Time to withdrawal will be defined as the number of days from the first open-label IMP intake date until the last IMP intake date for the open-label period. Patients who complete the open-label period will be censored at the date of end of the open-label period. A listing of patients, along with reasons for treatment discontinuation, will be provided with their relationship with Covid-19.

Additionally, the analysis populations for safety, efficacy, and pharmacokinetics (See [Section 2.3](#)) will be summarized in a table by number of patients on the enrolled population.

- Efficacy population
- Safety population
- Pharmacokinetics population.

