## 5 STUDY DESIGN

### 5.1 DESCRIPTION OF THE PROTOCOL

EFC11759 is a multicenter, randomized, double-blind, placebo-controlled, parallel-group study. It consists of:

- A screening period up to 4 weeks, designed to evaluate suitability to participate in the trial, in terms of MS diagnosis, MS treatment(s), and safety screening evaluations. No investigational medicinal product (IMP) is administered in this period.
- A double-blind treatment period of up to 96 weeks total duration for each patient
  - Patients are randomized to either teriflunomide or placebo at 2:1 ratio (110 patients on teriflunomide vs. 55 patients on placebo),
  - It includes a blinded PK run-in (8 weeks) phase consisting of 4 weeks of PK sample collection plus 4 weeks of analysis (corresponding to the first 8 weeks after randomization). The PK run-in (8 weeks) phase is intended to provide individual PK parameters to allow the dose adjustment to the 14mg adult-equivalent dose for the rest of the study from Week 8,
  - Patients experiencing a relapse after the PK run-in (8 weeks) and if confirmed by the Relapse Adjudication Panel (RAP) will have the option to continue in an open label period. If RAP does not confirm the relapse, the patient can continue in the double-blind phase or prematurely discontinue the treatment. Similarly, patients with high MRI activity (defined in [Section 8.1](#)) or completing the 96-week double-blind period will have the option to continue in the open label period.
- An open-label period for the remainder of 192 weeks after randomization

The open-label period will follow the double-blind period and last until 192 weeks after randomization. Its duration for a given patient will depend on when the patient enters this period. The duration of the open-label period will be 96 weeks for patients completing the 96-week double-blind period on treatment, and longer for patients switching to open-label during the initial 96 week double-blind period at the occurrence of a confirmed relapse or in case of high MRI activity.

It includes a blinded PK run-in phase (8 weeks, similarly to the double-blind period).

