2.3 ANALYSIS POPULATIONS

2.3.1 Enrolled population

The enrolled population is defined as patients who were randomized in the double-blind period and enrolled in open-label period analyzed according to the treatment group allocated by randomization in double-blind period (ie, placebo/teriflunomide versus teriflunomide/teriflunomide).

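### SAP 2.2 divides the double-blind disposition rows by the number of patients who entered open label, so those percentages have the wrong base or the rows omit patients

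*SAP*

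**What the plan says.** SAP section 2.2 says that "the total number of patients in each of the following categories will be presented in the clinical study report", and then lists the categories. Three of them describe the double-blind period:

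- "Patients who were randomized and treated in the double-blind period"
- "Patients who completed the double-blind period"
- "Patients who discontinued from the double-blind period"

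Patients enrolled in open label follow as a separate row, and then come the open-label treatment and discontinuation rows. One rule sets the base for the whole list: "For all categories of patients, percentages will be calculated using the number of enrolled patients as the denominator".

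The same section defines the base: "Enrolled patients are defined as any patient who entered the open-label period", with renewed consent or assent. Section 2.3.1 agrees: "The enrolled population is defined as patients who were randomized in the double-blind period and enrolled in open-label period". No other denominator is given for the double-blind rows. Section 2.2 also says that its tables are shown by the groups placebo/teriflunomide and teriflunomide/teriflunomide, and overall.

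Entry to open label is not automatic. Protocol section 5.1 says that patients "completing the 96-week double-blind period will have the option to continue in the open label period". It gives the same option after a confirmed relapse that follows the PK run-in, or after high MRI activity. Protocol section 9.8.6 requires consent to be repeated at entry.

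**The concern.** A disposition percentage should have a numerator drawn from its denominator. Here the denominator is fixed at a later point in the trial than three of the numerators. A patient who was randomized, treated and then left without entering open label belongs in the first double-blind row but not in the base.

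The table matters because the open-label report follows a selected group. SAP section 2.1.3.1 starts the clock for its primary endpoint at randomization, while sections 2.3.2 and 2.4.4 restrict the analysis to patients who enrolled and took open-label drug. A reader judging that selection needs the share of each randomized arm that entered. The disposition table is the natural place for it, and under the stated rule the enrolled row shows 100% in every group.

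**Working it through.** The documents state no disposition figure, so there is none to reproduce. The check applies the stated rule.

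**Inputs**
- R, randomized and treated: 165 as planned (110 teriflunomide, 55 placebo; SAP section 1.3), taking all as treated.
- E, enrolled in open label: not given in the documents. It cannot exceed the number randomized (SAP section 2.3.1), and entry is optional (Protocol section 5.1). A range is assumed below.
- X, the count in any double-blind row.

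**Formulas**
- Percentage under the SAP rule: X/E.
- Percentage on the natural base: X/R.
- Ratio of the two: (X/E) / (X/R) = R/E. It is the same for all three double-blind rows and exceeds 1 as soon as E is below R.
- Enrolled row under the SAP rule: E/E = 100% always. On the natural base: E/R.

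**Literal reading, with total counts in each row**

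| Not entering (assumed) | E | Randomized and treated, SAP rule | Enrolled row, SAP rule | Enrolled row, base R |
|---|---|---|---|---|
| 0 | 165 | 165/165 = 100.0% | 100% | 100.0% |
| 8 | 157 | 165/157 = 105.1% | 100% | 157/165 = 95.2% |
| 16 | 149 | 165/149 = 110.7% | 100% | 149/165 = 90.3% |

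The factor is 1/0.95 = 1.05 at exactly 95% entry and 1/0.90 = 1.11 at 90%. As an illustration, a completed or discontinued row holding 40% of R would print as 40/0.95 = 42.1% or 40/0.90 = 44.4%.

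**Restricted reading, with only enrolled patients counted in each row**
- Randomized and treated: E/E = 100% by construction.
- The completed and discontinued rows describe only patients who went on to open label.
- Patients who left without entering appear in no row. The R − E non-entrants (8 or 16 in the examples above) are lost from the table, and E/R cannot be recovered from it.

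The two faults are alternatives. Inflated percentages belong to the literal reading and missing patients to the restricted one. No reading of the sentence gives correctly based double-blind rows for everyone treated, unless every treated patient entered.

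**The case against.** The strongest reply is that the table was meant to cover enrolled patients only. The group labels placebo/teriflunomide and teriflunomide/teriflunomide suit only patients who reached open label, and section 2.2 ends by tabulating the analysis populations on the enrolled population. On that reading nothing exceeds 100% and no row is inflated. This stands far enough that percentages above 100% cannot be called a certain result. The request for total numbers per category, with enrolled patients as a later row of their own, points the other way. The restricted reading also has its own defect, because patients who left before open label disappear.

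A second reply is that double-blind disposition belongs elsewhere. The introduction to SAP section 2 refers the double-blind analysis to a separate SAP, and Protocol section 5.1 assigns that period to the first study report. That stands: the separate SAP is not among the documents, so nobody can conclude that correctly based double-blind rates go unreported in the trial as a whole.

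A third reply is that the table is descriptive and, on the literal reading, a row above 100% would be noticed and could be corrected from the counts. That also stands, and it limits the importance of the point without making the rule right.

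**Conclusion.** The point holds as a minor error in a stated rule. On the literal reading, the three double-blind percentages are too large by R/E, about 1.05 at 95% entry and 1.11 at 90%. On the restricted reading, the rows leave out the patients who did not enter. The literal result rests on at least one treated patient not entering, which is likely given optional entry and renewed consent. Its size rests on assumed entry rates.

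A reader might infer more than the documents support:

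- *That the share entering open label is hidden.* On the literal reading both counts are printed, so it is one division away; only the percentage is missing.
- *That randomized and treated would print 125%, and discontinuation 25% instead of 20%.* This takes the 20% non-relapse discontinuation in SAP section 1.3, gives 33 of 165 leaving and 132 entering, and computes 165/132 and 33/132. The 20% is a sample-size assumption, not an entry rate. The example also assumes that patients who switch early are not counted as discontinued. Section 2.2 does not say, and Protocol section 11.4.4.1 describes those leaving for high MRI activity as discontinuing double-blind treatment. The classification changes the discontinued count but not the factor R/E.
- *That the two arms would be distorted unequally.* This needs unequal entry. Entry of 50 of 55 and 90 of 110 would give factors of 1.10 and 1.22, but those counts are hypothetical.

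No efficacy or safety estimate, test or analysis population uses this denominator.

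**What to change.** In SAP section 2.2, replace the single-denominator sentence with text that states:

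1. The three double-blind rows count all randomized-and-treated patients of the same arm who meet the category, with that arm's randomized-and-treated number as the denominator.
2. The row for enrollment in open label uses the same denominator, so that it shows the share of each arm that entered.
3. Rows that start from open-label enrollment use enrolled patients as the denominator.
4. Whether patients who switch to open label after a confirmed relapse or high MRI activity count as completed or discontinued in the double-blind rows.

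For the first two items, the column labels should refer to the randomized arm, so that patients who never entered open label have a place in the table. The cost is a few sentences in the SAP and a change to one table shell. No new data and no new analysis are needed.

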#### **10.1.4 Post drug elimination follow up visits**

Two post-washout follow up visits should be scheduled 2 weeks and 4 weeks after study medication discontinuation and initiation of the washout procedure. These visits are not required in case the patient receives commercial product immediately after the study end.

The following items will be checked/performed and recorded at Visit 21 (EOT+2W) and Visit 22 (EOT+4W):

- Adverse events reporting.
- Concomitant medications.
- Vital signs (BP, HR, body temperature and weight).
- Physical examination at EOT + 2 Weeks only.
- ECG should be performed only for patients who had new abnormalities on the EOT ECG.
- Clinical safety laboratories
  - Hematology and differential panel,
  - Liver function panel,
  - Pancreatic enzyme tests,
  - Uric acid and inorganic phosphorus.
- Post-washout PK sampling (note that the EOT+4W PK sample should be taken even if the EOT+2W PK sample is under 0.02 µg/mL, to document stability level as per EU SmPC).

In case of adverse events AE/abnormal laboratory values, or teriflunomide level > 0.02 µg/mL after the elimination treatment, follow up until resolution should be planned.

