2.1.4 Safety endpoints

The safety analysis will be based on the reported adverse events and other safety information, such as clinical laboratory data, vital signs, ECG, etc.

Observation period

The observation period of the open-label period will be divided into 3 epochs:

- The **treatment** epoch is defined as the time from the first administration of the IMP in the open-label period to the last administration of the IMP in the open-label period.
- The **accelerated elimination** epoch is defined as the time from 1 day after the open-label treatment epoch up to 4 weeks (28 days) after the last administration of the IMP in the open-label period or up to the first administration in optional additional extension period, whichever occurs first.

The treatment-emergent adverse event (TEAE) period will include both treatment and accelerated elimination epochs.

- The **posttreatment** epoch is defined as the period of time starting from the day after the end of the treatment-emergent adverse event period up to the end of the open-label period (defined as the first dose of optional additional extension IMP for patients enter optional additional extension period, or the last protocol-planned visit, EOT +4W, in the open-label period or the resolution/stabilization of a followed-up AE for patients do not enter).

The on-study observation period is defined as the combination of TEAE period and posttreatment epoch.

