180	OL Visit 33	1219 - 1302	1240 - 1281	1219 - 1302
186	OL Visit 34	Not applicable	1282 - 1323	Not applicable
192	OL Visit 35	1303 - end of open-label period ^c	1324 - end of open-label period ^c	1303 - end of open-label period ^c

^a Schedule A includes: Coagulation panel (prothrombin time, and activated partial thromboplastin time); Complete chemistry panel (glucose, creatinine, BUN, sodium, potassium, chloride, bicarbonate, magnesium, calcium uric acid, LDH, alkaline phosphatase, inorganic phosphorus, total protein, albumin, globulin, albumin/globulin ratio, triglycerides, cholesterol and CPK. Urinalysis (pH, ketones, protein, glucose, blood, urobilinogen, bilirubin, microscopic sediment, specific gravity).

^b Schedule B includes: Hematology and differential panel (hemoglobin, hematocrit, red blood cell count, mean corpuscular hemoglobin, white blood cell count, neutrophils, lymphocytes, monocytes, eosinophils, basophils, platelets); liver function tests [ALT, AST, GGT, total bilirubin, and direct/indirect bilirubin] and pancreatic enzymes [serum amylase and lipase]).

^c End of open-label period is defined as later of the last open-label visit date or before 1st dose date in the optional additional extension period.

^d If remote visits, only weight will be collected for vital signs. Assessment date should be collected separately for weight and other assessments.

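### The open-label discontinuation curve times events at last dose but censors completers at the end of the period, which lowers it slightly after about open-label Week 96

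*SAP*

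**What the plan says.** SAP 2.2 (Disposition of patients) defines time to withdrawal as "the number of days from the first open-label IMP intake date until the last IMP intake date for the open-label period". For those who do not withdraw, it says: "Patients who complete the open-label period will be censored at the date of end of the open-label period".

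The end of the open-label period is defined in two places.

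- SAP 2.1.4 (Safety endpoints, observation period): for patients who do not enter the optional extension it is "the last protocol-planned visit, EOT +4W, in the open-label period or the resolution/stabilization of a followed-up AE for patients do not enter". For those who enter, it is "defined as the first dose of optional additional extension IMP for patients enter optional additional extension period".
- SAP 2.5.3, Table 7, footnote c: it is the "later of the last open-label visit date or before 1st dose date in the optional additional extension period".

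Protocol 10.1.4 adds an exception for the two post-elimination visits: "These visits are not required in case the patient receives commercial product immediately after the study end".

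The relapse analyses in SAP 2.4.4.1 and 2.4.4.2.1 use another rule. Patients without a relapse are censored at their last IMP administration.

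**The concern.** The event is permanent discontinuation of the drug, and it is dated by the last dose. A patient who has finished open-label treatment can no longer have that event. Under SAP 2.2 read with SAP 2.1.4, some completers nevertheless stay in the risk set until a date about 4 weeks or more after their last tablet.

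If every patient finished at the same open-label day, this would only lengthen the end of the curve. Here completion times are spread out. Patients who completed the double-blind period have 96 planned open-label weeks, and early switchers have up to 184. Completers who finish at Week 96 therefore enlarge the denominator for early switchers who are still on drug and can still discontinue. Each later discontinuation is divided by too large a number, and the error can only go one way: persistence on treatment looks slightly better than it is. At stake is the accuracy of the late part of the planned curve of discontinuation over time.

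**Working it through.** **1. Plan figures reproduced.** Shortest planned open-label duration: 192 − 96 = 96 weeks (Protocol 5.1). Longest: 192 − 8 = 184 weeks (Protocol 1.4, footnote s; SAP Appendix C, footnote r). Planning hazards (SAP 1.3): −ln(1 − 0.60)/2 = 0.4581 per year for placebo, half of which is 0.2291. The 2-year teriflunomide relapse rate is 1 − exp(−2 × 0.2291) = 36.8%. All agree with the documents, which give no figure for the discontinuation curve itself.

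**2. Who has a gap between last dose and censoring?**

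- Enters the optional extension: censored at the first extension dose under SAP 2.1.4, so little or no gap.
- Goes straight to commercial product: EOT+2W and EOT+4W visits not required, so little gap unless an adverse event is being followed.
- Neither: censored at EOT+4W or at resolution of a followed adverse event, so about 4 weeks or more.

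**3. Where on the curve?** Visit windows aside, no completer finishes before open-label Week 96. Up to then the two censoring rules give the same risk sets and the same curve.

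**4. Hand check at Week 100.** Assume 20% discontinuation in 2 years, borrowed from the planning assumption in SAP 1.3; the documents give no open-label rate.

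- Weekly hazard h = −ln(0.8)/104 = 0.002146.
- Still on drug at Week 96: exp(−96h) = 0.814.
- True rise from Week 96 to Week 100: 0.814 × (1 − exp(−4h)) = 0.0070, or 0.70 points.
- Under the planning hazards, 58% of simulated open-label entrants have exactly 96 planned weeks. If all who complete then stay in the risk set for 4 more weeks, only about 42% of it is on drug, and the curve rises by about 0.42 × 0.70 = 0.29 points.
- Shortfall: 0.70 − 0.29 = 0.41 points.

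**5. Simulation over the whole curve.** About 400,000 patients were simulated, with 2:1 allocation, switching after Week 8 at the planning hazards, and 20% double-blind dropout in 2 years. Kaplan-Meier was computed twice on the same data. With 20% open-label discontinuation and a 4-week gap for all completers:

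| Open-label week | Censored at last dose | Censored 4 weeks later | Shortfall (points) |
|---|---|---|---|
| 48 | 9.76% | 9.76% | 0 |
| just before 96 | 18.53% | 18.53% | 0 |
| 100 | 19.24% | 18.83% | 0.41 |
| 120 | 22.69% | 22.17% | 0.52 |
| 144 | 26.58% | 25.87% | 0.71 |
| 180 | 31.93% | 30.35% | 1.58 |

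The Week 100 row agrees with the hand check.

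**6. Range over the assumptions.** Shortfall in points with a 4-week gap:

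| 2-year discontinuation | Completers with the gap | Week 100 | Week 144 | Week 180 |
|---|---|---|---|---|
| 10% | all | 0.2 | 0.4 | 0.9 |
| 20% | all | 0.4 | 0.7 | 1.6 |
| 20% | half | 0.3 | 0.4 | 0.9 |
| 40% | all | 0.7 | 1.1 | 2.2 |

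**The case against.** **The governing definition is not certain.** SAP 2.1.4 defines the end of the period in order to bound the posttreatment safety epoch, and SAP 2.2 does not refer to it. Table 7, footnote c, gives the last open-label visit, with no extension for adverse-event follow-up. The two can coincide for a patient whose last visit is EOT+4W and differ for others. This stands: the text supports an ambiguous end date, and under some readings the gap is small. It is also a reason to name the last dose, because the result then no longer depends on which definition is programmed.

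**Not every completer is affected.** Extension entrants and patients going straight to commercial product have little gap. The documents do not give the share of the rest. This stands, and the half-of-completers row reflects it.

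**The shift is small against sampling error.** In 3000 simulated trials of 165 patients all entering open label, with a 28-day gap for all completers, about 29 patients were at risk at Week 144. The estimate had a standard deviation of 4.7 points there, against a shift of about 0.6 to 0.7. At Week 180 about 8 were at risk, with a standard deviation of 6.5 points against a shift of about 1.3. This also stands: the shift is largest where the curve is least well estimated.

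**No decision rests on it.** The curve is descriptive, with no planned test. Counts, percentages and reasons for discontinuation in SAP 2.2 remain correct.

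A reader might infer more: that discontinuation is understated along the whole curve, or that adverse-event follow-up makes the shortfall much larger. The documents support neither. The curve is identical up to about Week 96, and no document gives the length of adverse-event follow-up or the number of completers concerned.

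**Conclusion.** The point holds in limited form. Events and censoring use different clocks. Where there is a gap, the direction of the bias needs no assumption, since off-drug patients in the risk set can only lower the cumulative incidence. There is no effect before about open-label Week 96. After it, the shortfall is roughly 0.2 to 2 points with a 4-week gap for all completers, and about 0.3 to 0.9 points at 20% discontinuation if half have the gap.

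These sizes rest on three things that the documents do not supply: the open-label discontinuation rate (10% to 40% in 2 years assumed), the share of completers with a gap, and its length. They also rest on the planning relapse hazards for the timing of early switches. The relapse analyses are unaffected because they already censor at last dose. This is a minor correction to a descriptive display.

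**What to change.** In SAP 2.2, replace the censoring sentence with one stating that patients who complete open-label treatment are censored at their last open-label IMP intake date. That puts events and censoring on one clock and matches SAP 2.4.4.1 and 2.4.4.2.1, whose fallback for a missing EOT-page date (the last date on the IMP administration page) can be adopted too. Separately, align the definitions of the end of the open-label period in SAP 2.1.4 and in Table 7, footnote c, or state which analysis each one serves.

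The cost is one sentence for the censoring rule and a short edit to the definitions. The last-dose date is already collected, so no new data are needed.
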